Only a handful of therapeutic agents for PSC have undergone clinical trials, possibly due to low disease prevalence. None of the agents studied have shown a beneficial effect on clinically important endpoints and survival in PSC.¹⁷ Ursodeoxycholic acid (UDCA) is the single most extensively studied agent in PSC. However, large randomized and controlled prospective clinical trials have failed to demonstrate that UDCA can positively affect patient outcome.^{18,19} Further, the safety of long term use of high-dose UDCA in PSC patients has been questioned, as it has been associated with increased rates of serious adverse events.^{19,20} The American Association for the Study of Liver Disease (AASLD) recommends against the use of UDCA in PSC patients.⁷

Liver transplantation remains the sole treatment for end-stage PSC. There are several current avenues of research addressing treatment strategies for PSC. One target is the farnesoid X receptor, which plays a key role in bile acid homeostasis. Other evidence suggests a link with the intestinal microbiota,²¹ leading to the investigation of fecal transplantation and probiotics as therapeutic approaches. A very promising therapy is the use of oral vancomycin. In addition to its potential effects on microbiota, work by Abarbanel *et al.*²² suggests that its therapeutic properties in PSC are linked to immunomodulatory effects on regulatory T cells.

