These results will help us:

- Establish feasibility of the hypothesis that VC will play a therapeutic role in treatment of PSC
- Gain insight into the effect of VC on profiles of the proinflammatory cytokines IL-17 and IFNy
- Pave the way for more comprehensive clinical studies

Study Design and Methodology

This pilot study will be a 6-month, 30-subject clinical trial to assess the effects of VC on a surrogate biochemical endpoint known to have relevant association with clinical outcomes in PSC. All endpoint tests chosen are rapid, inexpensive, and minimally invasive. Due to the low prevalence of PSC, the study will be a single-arm, open-label study. The study will be undertaken at two sites, Mayo Clinic, Rochester, Minnesota (20 subjects) and Mayo Clinic, Phoenix, Arizona (10 subjects), both of which are tertiary referral centers for PSC. Immunic AG, a biotechnology company based in Munich, Germany, will supply the study agent in sufficient quantities for the study (see Letter of Support from Immunic AG). We have confirmed through consultation with NIH personnel that this is permissible under this funding opportunity.

During the 6-month treatment period, subjects will receive 30 mg VC orally once daily, a dose determined to be both safe and therapeutically relevant based on previous clinical studies (see Table 1). This will be preceded by a lead-in dosing period where subjects will receive 15 mg VC once daily for 1 week. Lead-in dosing is used to minimize the risk of drug intolerance during the initial treatment period. While no clinically relevant adverse events have been noted at 30 mg once daily dosing, in rare instances potentially drug-related hematuria has been observed in the first few days of treatment at higher doses (≥ 70 mg/day). As a precaution, subjects will be monitored for two weeks after initial drug

exposure for elevated erythrocytes in the urine by a dipstick test. It is not anticipated that hematuria will be seen if it has not developed within the first two weeks of drug exposure.

The following endpoints will be assessed at various times during the study and compared with baseline:

- i. Primary endpoint:
 - a. Improvement of serum alkaline phosphatase (ALP) [baseline, 3 months, and 6 months]
- ii. Secondary endpoints:
 - a. Bilirubin, Total and Direct [baseline, 3 months and 6months]
 - b. AST and ALT (aspartate and alanine transaminases) [baseline, 3 months, and 6 months]

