Due to the relatively low prevalence, it is possible that 30 subjects meeting inclusion criteria cannot be recruited within the planned 6-month recruitment period or that they are not split roughly equally between the two sites. In that case, we will extend the recruitment period and if required, we will execute the study with as few as 20 subjects, regardless of the distribution between sites. After the study is complete, further research may reveal other potentially interesting biomarkers that should be examined and thus we have included storage of extra blood draws during the study. Given the pilot nature of this study, it is possible that benefits are seen even though results are not conclusive. Study data may be examined more carefully to determine if benefits occur in a distinct subpopulation of subjects (e.g. in PSC patients with UC versus those without).

Overall, considering the known safety data, the implemented risk minimization measures, the expected benefits in the target population, and the unmet medical need for treatment in PSC, the risk-benefit evaluation is considered favorable.

PROTECTION OF HUMAN SUBJECTS

This Human Subjects Research meets the definition of a clinical trial.

I. Risks to Human Subjects

a) Human Subjects Involvement, Characteristics, and Design: A total of 30 adults (age range 18-75 years) who meet the criteria for diagnosis of primary sclerosing cholangitis (PSC), as defined by the American Association for the Study of Liver Diseases (AASLD) published guidelines, will be enrolled into this study from two centers. PSC patients with and without inflammatory bowel disease (IBD) will be included. Other inclusion and exclusion criteria are detailed below:

Inclusion Criteria

- a. Male or female subject age 18-75 years
- b. Diagnosis of PSC consistent with the guidelines published by the AASLD. All subjects must have an elevated serum ALP of at least 1.5 times upper limit of normal (ULN) at baseline plus cholangiographic evidence of PSC (MRI, endoscopic retrograde cholangiography, or direct cholangiography).
- c. Indirect bilirubin <1.2 times the ULN
- d. An ultrasound (or equivalent imaging modality) that excludes biliary obstruction and malignancy within 6 months of study enrollment
- e. PSC with or without inflammatory bowel disease, such as ulcerative colitis or Crohn's disease
- f. Must agree to comply with the study protocol and provide informed consent

Exclusion Criteria

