Overall, the safety profile at the dosage level to be used in this trial is quite positive. An in-depth analysis of the entire clinical database demonstrates that vidofludimus at daily doses below 70 mg is not associated with an increased rate of clinically relevant adverse reactions, including hematuria, relative to placebo. These studies include 233 subjects with rheumatoid arthritis, Crohn's disease, or ulcerative colitis who received daily doses of vidofludimus 20 mg (~3000 treatment days) or vidofludimus 35 mg (~16,500 treatment days) in 3 clinical trials with individual treatment durations of 12-13 weeks.

The investigator will open an IND for the proposed clinical trial. Immunic AG, the drug supplier, will allow the investigator to reference Immunic's IND for vidofludimus calcium (see Letter of Support from Immunic).

2. Protections against risks related to the disease to be studied (PSC either in the absence or the presence of IBD): Acute ascending cholangitis, an acute biliary infection with high mortality rates, is a risk in patients with PSC. Study subjects will be asked about symptoms/signs of ascending cholangitis during clinic visits and phone calls, and subjects will be provided with a list of symptoms and instructed to report the symptoms to the study coordinator immediately if they arise. Symptoms suggestive of acute ascending cholangitis or biliary tree stricture include new onset jaundice, abdominal pain, dark urine, and light-colored stools. Study subjects will be advised to come to the clinic for evaluation or visit the nearest emergency room for consultation with an emergency room physician. If clinical suspicion for acute ascending cholangitis is high, the course of action may include aggressive antibiotic therapy and relief of biliary obstruction (via percutaneous, endoscopic, or surgical intervention), with or without a hospital stay. The Tokyo guidelines are commonly used for the diagnosis of acute ascending cholangitis.

The Tokyo criteria are:

- i. Two of three (fever, right upper quadrant pain, and jaundice), plus
- ii. Systemic inflammation (elevated white blood count and/or C-reactive protein), plus
- iii. Abnormal liver function tests, plus

iv. Imaging detection of biliary dilatation and etiology (stone, stricture, stent, neoplasm)

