Cholangiocarcinoma (CCA) is one of the most serious complications of PSC. Screening for CCA is currently recommended every 6-12 months (by liver ultrasound or MRI) as part of standard of care for PSC patients. Patients with CCA at screening will be excluded. If during the course of the study CCA is suspected, subjects will undergo the necessary evaluations (which is part of standard of care) to exclude CCA.

As PSC is frequently associated with IBD, study subjects will undergo clinical assessment for IBD at clinic visits and by phone between these visits. Study subjects should report any new symptoms of an IBD flare to the study coordinator. These symptoms include abdominal pain, fever, bloody stools, and an increase in frequency of bowel movements.

In subjects with UC, we will use the Ulcerative Colitis Clinical Score to assess the disease activity/severity. This score, a modification of the well-known Mayo Score, consists of 4 items: stool frequency, rectal bleeding, subject's functional assessment, and physician's global assessment (PGA). Scores range from 0 to 12 points, with higher scores meaning more active disease. The Short inflammatory Bowel Disease Questionnaire (SIBDQ) is a health-related quality of life HRQoL tool measuring physical, social, and emotional status in IBD patients. The SIBDQ contains 10 items with 4 dimensions: bowel symptoms (3 items); systemic symptoms (2 items); emotional function (3 items); and social function (2 items). The total score ranges from 10 (worst health) to 70 (best). The SIBDQ can be administered and scored quickly and easily.

In cases of confirmed *Clostridium difficile* colitis, any antibiotics the patient is already taking that are not specifically directed at *Clostridium difficile* will be reduced or stopped. Antibiotics such as vancomycin or other appropriate antibiotics specifically directed at *Clostridium difficile* will be administered. The use of immunosuppressive drugs should be minimized, but if required, patient will be closely monitored.

IBD, particularly ulcerative colitis, is an important risk factor for colorectal cancer. Currently, screening colonoscopy is recommended annually in patients with PSC and IBD.

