- Elevated total bilirubin $\geq 2 \times$ baseline that does not return to within 10% of baseline within two weeks
- Serious allergic reaction
- Pregnancy or breastfeeding

Non-adherence to the study protocol by a study subject may, at the discretion of the principal investigator, be grounds for termination.

Statistical Analysis Plan: The proportion of patients with normalization of serum ALP at 3 months and 6 months and their corresponding confidence intervals will be estimated using exact binomial method. The primary endpoint is ALP normalization (within the normal limits of the laboratory test) rate at 6 months. We will define success as a 95% CI that does not overlap 0 at 6 months. Further, we will further investigate if the absolute ALP decreases over time using mixed model with repeated measures to account for within patient correlation over time.

All the liver biochemistries and proinflammatory cytokine profile over time will be analyzed using mixed model with repeated measures to investigate how VC treatment plays a role over the 6 months duration. The liver biochemistries and proinflammatory cytokine will be dichotomized into abnormal and normal groups if possible and further the abnormal proportions at different time points will be estimated to see the trend over time.

The incidence, type and relatedness of serious adverse events and adverse events will be monitored and reported for all the subjects.

Adherence to Regulatory Standards: The investigators will ensure that this study is conducted in full conformity with Regulations for the Protection of Human Subjects of Research codified in 45 CFR Part 46, 21 CFR Part 50, 21 CFR part 56, and the ICH; Good Clinical Practice E6.

ClinicalTrials.gov Requirements: The principal investigator will ensure that this clinical trial is properly registered at www.clinicaltrials.gov, per the Public Law 110-85 (also known as the FDA Amendments Act (FDAAA) of 2007), no later than 21 days after the first subject is enrolled. The principal investigator will also ensure that the results (including adverse events) of this clinical trial are reported no later than 1 year after completion of the clinical trial.

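### No rule covers potentially PSC-active treatment, such as vancomycin, started after baseline, so a normal month-6 ALP that follows it counts as a vidofludimus response

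*Combined protocol and SAP*

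**What the plan says.** **Design and endpoint.** Under Study Design and Methodology, "the study will be a single-arm, open-label study". The planned size is 30, and under Risk Mitigation and Alternative Strategies "we will execute the study with as few as 20 subjects" if recruitment is slow. The Statistical Analysis Plan states: "The primary endpoint is ALP normalization (within the normal limits of the laboratory test) rate at 6 months". For the normalisation rates, "their corresponding confidence intervals will be estimated using exact binomial method", and success means that the 95% interval at 6 months excludes zero. ALP over time is also analysed with a repeated-measures mixed model.

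**Other treatments.** The Significance section says: "A very promising therapy is the use of oral vancomycin". Section II b) 2 (protections against disease-related risks) says that in confirmed C. difficile colitis "Antibiotics such as vancomycin or other appropriate antibiotics specifically directed at" that organism will be given. For suspected ascending cholangitis it foresees antibiotics and "relief of biliary obstruction (via percutaneous, endoscopic, or surgical intervention"). Table 7 lists both conditions among the expected adverse events.

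**Rules that come near the issue.** Inclusion d requires imaging that rules out obstruction. Exclusions l, t, u and v remove active cholangitis on antibiotics, recent or active C. difficile infection, and recently treated gut pathogens. Exclusions x and y limit methotrexate and rosuvastatin dose. Apart from the live-vaccine exclusion (w), which runs to the end of the study, these act at entry. UDCA appears only in the background. Neither the individual termination criteria nor the Statistical Analysis Plan mentions treatments started after baseline.

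**The concern.** A single-arm trial has no control group in which the effect of other treatments would also appear, so the whole change from baseline is read as a drug effect. The plan names a treatment that it regards as promising in PSC and foresees its use during follow-up. It then gives the analyst no basis for treating a later ALP value differently. If the rule is followed as written, a patient given vancomycin at month 4, say, whose ALP is normal at month 6 is a responder. A decision to discount that patient afterwards would be made in an open-label study with the results known.

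The trial is meant to inform whether larger studies are warranted. What is at stake is a positive signal that rests on a patient whose ALP fell for another reason.

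**Working it through.** The plan gives no null rate, power or sample-size derivation, so there is no stated figure to reproduce. The check applies the plan's own success rule.

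**Inputs from the documents:** N = 30 (minimum 20); exact binomial 95% CI; success if the interval excludes 0; entry ALP at least 1.5 x ULN; response = ALP within normal limits at month 6.

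**Step 1: how many normalisations give success?** For x = 1 the exact lower limit is 1 - 0.975^(1/N). For x = 0 the lower limit is 0 and the upper limit is 1 - 0.025^(1/N).

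| N | Normalised | Exact 95% CI | Success? |
|---|---|---|---|
| 30 | 1 | 0.08% to 17.2% | yes |
| 30 | 0 | 0% to 11.6% | no |
| 20 | 1 | 0.13% to 24.9% | yes |
| 20 | 0 | 0% to 16.8% | no |

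If the only normalisation followed another active treatment, the classification of that one patient decides the trial.

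**Step 2: how often might that happen?** The documents give no rate. Let q be the chance that a patient's month-6 ALP is normal because of another treatment (assumption). With an inert drug and no other normalisations, P(success) = 1 - (1 - q)^N.

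| q (assumed) | N = 30 | N = 20 |
|---|---|---|
| 0.5% | 14.0% | 9.5% |
| 1% | 26.0% | 18.2% |
| 2% | 45.5% | 33.2% |
| 5% | 78.5% | 64.2% |

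**Step 3: how large must the fall be?** From the entry minimum, normalisation needs a fall of 1 - 1/1.5 = 33%. A 30% fall leaves 1.5 x 0.70 = 1.05 x ULN, which is not a response. A 40% fall normalises only baselines up to 1/0.60 = 1.67 x ULN, and a 50% fall only up to 1/0.50 = 2.0 x ULN. So q is the chance of starting such a treatment multiplied by the chance that it normalises ALP, and the second factor may be well below 1.

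**Step 4: the continuous scale.** If k of 30 patients have such treatment and it lowers their ALP by a fraction d (assumption), the apparent fall in geometric mean ALP with no drug effect is 1 - exp[(k/30) ln(1 - d)]. For d from 0.3 to 0.5 this is 1% to 2% (k = 1), 4% to 7% (k = 3) and 6% to 11% (k = 5). The distortion is small unless several patients are affected, and nothing in the documents supports k = 5.

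**The case against.** The strongest case on the other side has five parts.

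- **Direction.** A reader might infer that all such treatment favours the drug, including biliary drainage. The documents do not support that. Obstruction and active cholangitis are screened out at entry, so a new obstruction would be expected to worsen liver tests, and drainage may only bring ALP back toward baseline. Stopping or reducing a treatment could raise ALP. This stands.
- **Evidence of an ALP effect.** No section says that UDCA or drainage lowers ALP. For vancomycin the background claims promise in PSC and effects on regulatory T cells, but gives no ALP figure. The C. difficile text gives no route or duration. This stands as a limit on size. It does not explain the absence of a rule for a treatment that the protocol itself regards as promising.
- **Automatic false responders.** A reader might infer that any treated patient becomes one. Step 3 shows otherwise, and the protocol itself considers full normalisation unlikely in 6 months.
- **The one-patient threshold.** Success on a single normalisation, whatever its cause, is mainly a flaw in the success rule. This stands. Yet a stricter threshold would still count the affected patient.
- **Silence and treatment policy.** No text says that these patients are responders. Using the month-6 value whatever else was given is a recognised approach, and affected patients could be identified from Table 3 and the adverse event records. But that approach normally relies on a control arm, and recording the data does not link them to the endpoint.

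**Conclusion.** The concern holds in a bounded form. As written, the plan scores the month-6 ALP at face value, and no eligibility or analysis rule covers potentially PSC-active treatment started after baseline. Vancomycin is the best-supported case, because the protocol both calls it promising in PSC and foresees its use. Under the stated success rule one such patient could turn 0/30 (0% to 11.6%) into 1/30 (0.08% to 17.2%), and so change the conclusion.

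The frequency is an assumption throughout. So is any ALP effect of UDCA changes or drainage, and drainage could act in either direction. The documents do not support a claim that the trial's result will be biased by a given amount. They support the claim that the counting rule credits the drug with such a response, and that nothing pre-specified allows otherwise. The change should be made before the data are analysed.

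**What to change.** Add to the Statistical Analysis Plan, with no change to care, eligibility or visits:

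1. In the primary responder analysis, count as a non-responder any patient who starts or increases vancomycin, UDCA or another agent on a pre-listed set of PSC-directed treatments after baseline and before the month-6 ALP. Fix the list before analysis.
2. Report the rate with all observed values as a sensitivity analysis. Run the mixed model with and without ALP values recorded after such treatment.
3. Handle biliary drainage, and stopping or reducing such treatment, by sensitivity analysis only, because the direction of their effect is not established.
4. Report the number of patients affected and the baseline use of the listed treatments.

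**Cost:** SAP wording and one derived flag. Table 3 already schedules review of concurrent medications through the study, and adverse event records already capture interventions; start and change dates must be recorded. The response rate may be slightly lower, because a patient whose ALP was already normal before the other treatment began would count as a non-responder. The analysis in item 2 shows how much depends on that.

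This does not cure the lenient success threshold. Nor does it resolve the difference between normalisation in the SAP and the 25% ALP improvement (with its AST condition) in Study Design and Methodology. The same flag works with either definition.
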